### Safety population

The safety populations are identical to the modified ITT populations.

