## 8.5 Treatment Status Update Form

2-weeks after the participant has been enrolled, the site staff should submit the Treatment Status Update Form via <https://redcap.partners.org>. The Treatment Status Update Form will ask sites to report: (1) whether or not the participant is receiving treatment in accordance with the treatment arm to which s/he was assigned (see next paragraph for more information); (2) if yes, which anticoagulation drug is the participant receiving; (3) if no, why not (e.g., due to insurance non-coverage, patient refusal, transfer of care, receive no anticoagulation therapy, other); (4) if no, which anticoagulation drug is the participant receiving, if any.

If participant is not receiving treatment in accordance with the treatment arm to which s/he was assigned, that is NOT a protocol violation. Please keep this patient ON STUDY.

- Arm 1: Switching between DOACs is allowed
- Arm 2: Switching between LMWH/warfarin is allowed
- Anticoagulation “breaks” and “gaps” are not protocol violations
- Arm 1: Switching to LMWH is discouraged but is not a protocol violation.
- Arm 2: Switching to DOAC is discouraged but is not a protocol violation
- Record abstraction and medication diaries will ascertain these rates

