## 3.2. Definition of analysis populations

### Intention-to-Treat (ITT) population

The intention-to-treat population for the randomized cohort includes all randomized subjects. The corresponding population for the preference cohort consists of all patients who would not be randomized but participated in this study. The corresponding population for the full cohort consists of all randomized subjects and all subjects in the preference cohort. In the analyses with the ITT population, we performed the analyses by group, using the assigned treatment group indicator regardless of whether the subject received the assigned treatment or not.

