### Modified Intention-to-Treat (ITT) population (Primary analyses)

Based on the data review performed before conducting the final analysis, we found that quite a few subjects in this pragmatic trial did not receive treatment according to their assigned group. In the ITT population, those patients who received treatment in the group opposite to the one to which they were randomized would also be included in the analysis. Based on the concern that these subjects could cause a potential bias toward the noninferiority claim with the ITT analysis, we have defined a modified ITT population. In order to be conservative with regard to testing the non-inferiority hypothesis, the primary analyses will rely on the modified ITT population. The modified ITT population includes all subjects who received a study drug according to their assigned treatment group and participated in this study.

The modified ITT population for the randomized cohort includes all randomized subjects who received at least one dose of the anti-coagulation treatment strategy to which they were assigned. The preference modified ITT population includes all non-randomized subjects who received the anti-coagulation treatment which they preferred subsequent to informed consent to study participation. The full modified ITT population includes the sum of the two aforementioned categories (randomized cohort and preference cohort).

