### Per-protocol population

The per-protocol population includes those patients who received a study drug of the assigned treatment group and do not have any major protocol violations.

The randomized per protocol population includes those subjects who received a study drug according to the randomized treatment assignment and do not have any major protocol violations. The preference per protocol population includes those subjects who were not randomized and received a study drug according to the subject's preference and do not have any major protocol violation. The full per protocol population is the sum of the two aforementioned categories.

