### 6) Sensitivity Analyses using the ITT and the per protocol populations.

Sensitivity analyses will be performed with alternative cohort specification.

We will repeat all the analyses using the ITT population and then using the per-protocol population.

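### Patients who took only the other arm's drug belong to no safety population, and the ITT repeat returns them for bleeding only, under the drug they did not take

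*Combined protocol and SAP*

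**What the plan says.** SAP section 3.2 defines four populations.

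- **ITT.** All randomized patients, analysed "using the assigned treatment group indicator regardless of whether the subject received the assigned treatment or not".
- **Modified ITT, the primary set.** For the randomized cohort it "includes all randomized subjects who received at least one dose of the anti-coagulation treatment strategy to which they were assigned". For the preference cohort it "includes all non-randomized subjects who received the anti-coagulation treatment which they preferred subsequent to informed consent to study participation".
- **Per-protocol.** Patients who "received a study drug of the assigned treatment group and do not have any major protocol violations".
- **Safety.** "The safety populations are identical to the modified ITT populations".

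The reason given for modified ITT is that "quite a few subjects in this pragmatic trial did not receive treatment according to their assigned group", and that keeping patients treated in the opposite group could bias an ITT analysis toward noninferiority.

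Among the secondary analyses of the primary endpoint (SAP 3.5.2.3, item 6) the SAP adds: "We will repeat all the analyses using the ITT population and then using the per-protocol population". SAP 3.6.2 carries those analyses over to major bleeding, and the major-bleeding analyses to the other bleeding grades. SAP 3.8.2 summarizes other serious adverse events by cohort, arm, grade and type, with Fisher's exact test, and names no alternative population. Protocol 8.5 has sites report at about two weeks, for a patient off the assigned arm, "which anticoagulation drug is the participant receiving, if any".

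**The concern.** A safety population is normally meant to hold everyone exposed to a study treatment. Here it is defined by agreement with the assignment. A patient assigned LMWH/warfarin who took only a DOAC, or the reverse, could bleed on a study drug and still be left out. The SAP's argument for modified ITT concerns the noninferiority test. It gives no separate reason for dropping exposed patients from the safety tables, although Objective 2 concerns the harms of each therapy and SAP 3.8.1 names major bleeding as the main safety endpoint.

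The exclusion also need not act equally on the two arms of this unblinded trial. Protocol 14.3 expects some patients to use LMWH while DOAC coverage is arranged. An Arm 1 patient whose DOAC never starts, and who stays on LMWH, leaves the safety set. An Arm 2 patient who takes LMWH briefly and then moves to a DOAC stays in it. The documents give no counts from which to judge whether this happened unevenly.

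**Working it through.** The plan states no figure on this point, so there is none to reproduce. The check is a trace of the definitions, followed by arithmetic under labelled assumptions.

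**Step 1. Follow a randomized patient who took only the other arm's drug.**

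| Population (SAP 3.2) | Included? | Grouped under |
|---|---|---|
| ITT | Yes | Assigned arm, i.e. the drug not taken |
| Modified ITT | No | – |
| Per-protocol | No | – |
| Safety | No (same as modified ITT) | – |

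For bleeding, the ITT repeat in SAP 3.5.2.3 applies through SAP 3.6.2. For other serious adverse events, SAP 3.8.2 has no such link: the ITT repeat is listed under the primary endpoint. Protocol 13.6 compares toxicity between the two strategies but names neither a population nor a grouping rule.

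**Step 2. How many patients could be missing?** The randomized total is 671 (SAP 2.5). The share c who took only the other arm's drug is not given, and neither is a bleeding risk. Both are assumed. Missing patients = 671 × c; missing bleeds = 671 × c × risk.

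| c (assumed) | Patients missing | Bleeds at 3% to 6% risk (assumed) |
|---|---|---|
| 2% | 13 | 0.4 to 0.8 |
| 5% | 34 | 1.0 to 2.0 |
| 10% | 67 | 2.0 to 4.0 |
| 15% | 101 | 3.0 to 6.0 |

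**Step 3. Does the ITT repeat stand in for a table by drug received?** Let p1 and p0 be the bleeding risks on DOAC and on LMWH/warfarin, and let a share c of each arm take only the other drug. Then

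ITT difference = [(1 − c)p1 + c·p0] − [(1 − c)p0 + c·p1] = (p1 − p0)(1 − 2c).

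With an assumed true excess of 3.0 points on DOAC, the ITT difference is 2.88, 2.70, 2.40 and 2.10 points at c = 2%, 5%, 10% and 15%. The point estimate falls below the 2.5-point bleeding margin of SAP 3.6.2 once c exceeds (1 − 2.5/3.0)/2 = 8.3% per arm. The formal test uses the upper confidence bound, so this shows only the direction: the ITT repeat dilutes a difference in harm.

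**Step 4. How far could an arm's bleeding rate move?** If an arm of n patients with b bleeds loses m patients who had x bleeds, the shift is b/n − (b − x)/(n − m). The arm size is taken as about 671/2, or 335.

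- *Same risk in the excluded.* At 8%, b = 0.08 × 335 = 26.8. Losing x = 4 bleeds means losing m = 4/0.08 = 50 patients. (26.8 − 4)/(335 − 50) = 22.8/285 = 8.0%. The shift is zero.
- *Higher risk in the excluded, all from one arm.* Let m = 34 with x = 4 (11.8%), and let the other 301 bleed at 6% (18.06). Then b = 22.06 and b/n = 22.06/335 = 6.6%, against 6.0% after exclusion. The shift is about 0.6 points.

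**The case against.** The best defence is that the gap is narrow. Everyone in modified ITT took at least one dose of the assigned strategy, so its bleeding tables place each patient under a class that patient did take. Capture of events is also intact. Protocol 12.3 requires expedited reports of all deaths and all grade 3 to 5 bleeds, by criteria that do not depend on the drug taken. Protocol 13.6 has adverse events reviewed monthly, and 13.9 provides for board review. The ITT repeat includes these patients for bleeding. All of this stands, and it limits the point to the final tabulations.

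Three stronger readings are tempting, and the documents do not support them.

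- *No table shows bleeding under a drug actually taken.* The modified ITT tables do so for their members. What they lack is the patients who took only the other arm's drug; they also leave later switchers under the assigned arm. For the protocol 13.6 comparison, a grouping by treatment received is unspecified, not ruled out.
- *Dropping 4 bleeds moves an arm's rate by 4/335 = 1.2 points, about half the margin.* That removes the bleeds but leaves their patients in the denominator. Done properly (step 4), the shift is about 0.6 points in an unfavourable example and zero at equal risk.
- *The number excluded must be large.* The SAP's remark on treatment not given as assigned carries no count. It may include patients who took no anticoagulant, a possibility listed in protocol 8.5, and they properly stay outside a safety set.

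The defence does not answer the gap in definition. Patients exposed only to the other arm's drug are in no safety set, and for other serious adverse events no stated analysis brings them back.

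**Conclusion.** The point holds in a limited form. Equating the safety population with modified ITT leaves out patients exposed only to the other arm's drug. The ITT repeat restores them for bleeding alone, under the wrong drug, and is not stated to reach the other serious adverse events.

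The size cannot be fixed from the documents. The range of 13 to 101 missing patients and about 0.4 to 6 bleeds rests on an assumed crossover share of 2% to 15% and an assumed bleeding risk of 3% to 6%. Any effect on a rate depends on how far the excluded patients' risk differs from that of the patients kept, and on whether exclusions differ by arm. Neither the primary VTE conclusion nor the 2.5-point bleeding comparison is affected. This is a cheap improvement to the safety reporting.

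**What to change.** In SAP 3.2, redefine the safety population as all enrolled patients who took at least one dose of any Arm 1 or Arm 2 anticoagulant after enrollment, grouped by treatment received under a stated rule:

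- a patient with at least one dose of the assigned strategy stays under that arm;
- a patient who took only the other arm's drug is grouped under that drug.

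A simpler rule based on the first class taken after enrollment would misclassify patients. Protocol 11.4.1 describes a parenteral lead-in for two of the DOACs, protocol 11.2 allows up to 14 days before protocol treatment starts, and protocol 14.3 foresees LMWH while coverage is awaited. Arm 1 patients following the plan would be labelled as LMWH. The two-week form also records current treatment, not the first drug.

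Use the new set for descriptive tables of bleeding by grade and of serious adverse events. In the CONSORT diagram, give by arm the number who took only the other arm's drug and the number who took nothing. Keep modified ITT and ITT for the 2.5-point noninferiority comparison.

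The cost is a change of SAP wording and one more set of tables. The data already come from the Treatment Status Update Form, the medication diaries and the six-month record abstraction. The drawback is that groups formed by treatment received are not protected by randomization, so the tables should be labelled descriptive.

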### 3.3. Disposition of study subjects

Following the CONSORT guideline a CONSORT diagram will be generated to describe the patient population by cohort with descriptions of the numbers of participants in the preference and randomized cohorts displayed side by side.

### 3.4. Baseline demographic and disease characteristics

Baseline patient characteristics and disease characteristics listed below will be summarized using descriptive statistics by group. The two-sample Wilcoxon test will be used for between-group comparisons of continuous variables and ordered categorical variables, and Fisher's exact test will be used for nominal categorical variables.

List of the variables:

- Age at enrollment [year]
- Age category (<65, >=65 year old)
- Sex (Male/Female)
- Race (Native American or Alaska Native/Asian/Black or African American/Native Hawaiian or other Pacific Islander/White/Unknown)
- Ethnicity (Hispanic or Latino/Not Hispanic/Unknown)
- Height [cm]
- Weight [kg]
- BMI
- Education level (Grade school or less/high school or GED/Some vocational, business or trade school/some college/college/some graduate school/graduate or professional degree)
- Whether out-of-pocket costs of anti-clotting drugs affect decision to participate in the study (not at all/a little/moderate/quite a bit/extremely)
- Payment (Private insurance/Medicare/Medicaid/Military or Veterans Sponsored/Self Pay/Other/Unknown)
- ECOG performance status (0/1/2/3/4)
- Smoking status (current/former/never)
- Cancer ever metastasized (Yes/No)
- HighlyThrombogenetic Tumors (Yes/No)
- Indwelling Central Venous Catheters (Yes/No)
- Thrombocytopenia (Yes/No) (<150,000/mm^3)
- Creatinine Clearance [ml/min] (Gender-specific Normal/abnormal)
- Albumin [g/dL] (<3.5mg/dL vs. >=3.5mg/dL)
- Self described global health status at baseline (excellent/very good/good/fair/poor)
- Current cancer Type (solid cancer vs hematologic cancer)
- Current cancer Subtype (Leukemia/Lymphomas/Blood Disorders, Breast, Gastrointestinal and Digestive, Gynecologic, Head and Neck, Neurological (Brain), Sarcoma, Skin/Melanoma, Thoracic (Chest/Lung), Genitourinary, Other)
- AJCC cancer stage at diagnosis (0, I, II, III, IV, Not applicable)
- Blood clot type (PE, DVT, Both, Unknown)
- The part(s) of the body where the blood clot found
  - Lung (Yes/No)
  - Leg (Yes/No)
  - Arm (Yes/No)

- Other (Yes/No)
- Site of index VTE diagnosis (inpatient hospital stay/outpatient appointment/emergency department/home/other)
- Site of index VTE first treatment (inpatient hospital stay/outpatient appointment/emergency department/home/other)
- First index VTE treatment prescribed (Warfarin/Dalteparin/Enoxaparin/Fondaparinux/Heparin/Other oral medication/Other injectable medication/Unknown)
- Previous VTEs and the number of prior VTEs (No, 1, 2, 3+)
- Bleeding at baseline (None, Mild, Moderate, Severe)

### 3.5. Primary endpoint evaluation

#### 3.5.1. Primary endpoint

The primary endpoint is cumulative VTE recurrence reported by either patients or their clinicians at 6 months. A recurrent VTE is synonymous with the cumulative incidence of any VTE irrespective of the anatomic site. Note that we will analyze the VTE recurrent event rate at 6 months but the data we will use to assess this primary endpoint is not a dichotomous variable that indicates the presence/absence of cumulative VTE recurrent events at 6 months. The analysis variable we will use for the primary endpoint is time from enrollment to occurrence of a VTE recurrent event. We will estimate the VTE recurrent event at 6 months using a time-to-event analysis with this analysis variable, where deaths are handled as competing risks and lost-to-followup patients are handled as censored observations (see Section 3.5.2.1 for details). This approach accounts for censored observations more appropriately than an analysis using a dichotomous variable, whereas it yields the same result if there are no censored observations.

#### 3.5.2. Analysis for the primary endpoint

##### 3.5.2.1. Primary analysis

The primary aim of this study is to compare the intervention and comparator arms with respect to their ability to prevent recurrent VTE. Because the intervention (DOAC therapy) is more easily administered than the comparator (usual care with LMWH warfarin), DOAC is expected to have higher adherence and therefore decreased incidence of VTE. Accordingly, a noninferiority design with a superiority alternative is preferred, as described by Friedlen et al. The primary analysis will test the noninferiority of the DOAC therapy with the primary analytic cohort (modified ITT population of the randomized cohort). If noninferiority is demonstrated, superiority of the DOAC therapy will be tested.

Because VTE is often a proximate cause of death in cancer patients' unexplained sudden demise, but diagnostic procedures are rarely performed (post-mortem scans, autopsies, etc.), we considered VTEs that were clinically significant as the primary outcome on the basis of an antemortem diagnosis. Separately, we looked at all-cause deaths because deaths from cancer and deaths from VTE are difficult to distinguish. Cancer patients routinely die at home and it is not possible to determine whether the proximate cause of death was a VTE, progression of tumor or some other cause. Indeed, the cause of many deaths in cancer patients is multifactorial. We will estimate the cumulative incidence of recurrent VTE at 6 months using standard competing risk analysis methods, where death will be treated as a competing risk. We calculate the difference in the 6 months incidence rate between groups and the corresponding 0.90 confidence interval (CI).

#### 1) Noninferiority test of DOAC

The hypothesis for testing the noninferiority of the DOAC strategy is that the difference in the primary endpoint at 6 months is no greater than a noninferiority margin of 3% for the intervention-comparator. This noninferiority margin was selected based on what is acceptable to patients based on patient-stakeholder input as well as on input provided by clinicians

To confirm the noninferiority hypothesis, we will construct a two-sided 90% confidence interval (CI) for the difference in the cumulative incidence of the primary endpoint at 6 months (180 days). If the upper bound of the CI is less than 3%, we will conclude that the DOAC management strategy is non-inferior to the LMWH/warfarin strategy for management of VTE in patients with cancer.

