**Glossary of abbreviations**

AFT -- Alliance Foundation Trials, LLC  
CI -- Confidence Interval  
CNS -- Central Nervous System  
DOAC -- Direct Oral Anticoagulants  
DVT -- Deep Vein Thrombosis  
ITT – Intention-to-Treat  
LMWH -- Low Molecular Weight Heparin  
PE -- Pulmonary Embolism  
SD – Standard Deviation  
SE – Standard Error  
RCT – Repeated Confidence Interval  
VTE -- Venous Thromboembolism

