## 3. Analysis methods and presentation

### 3.1. General principles

Analysis will be performed on the preference cohort and the randomized cohort separately. Where appropriate, variables will be summarized descriptively (frequency counts and percents for categorical variables, and counts, means, standard deviations (SD), medians, minimums, maximums, etc., for continuous variables) for two treatment groups – DOACs and Control. The primary analysis cohort is the randomized cohort. The secondary analysis cohort is the preference cohort. Using meta-analysis technique, the results from two cohorts will be combined.

We will construct 90% two-sided confidence intervals (CI) for the between-group comparisons for the analyses of VTE, bleeding, and mortality. A 90% two-sided CI corresponds to conducting a statistical test at a one-sided 5% significance level. For the other analyses, all confidence intervals, statistical tests, and resulting p-values will be reported as two-sided and assessed at the 5% significance level. If the computed lower confidence bound for proportion variables is less than -1, then the lower bound is defined as -1. If the computed upper confidence bound for proportion variables is greater than 1, then the upper bound is defined as 1.

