## 2) Superiority test of DOAC

If noninferiority of DOAC is demonstrated, a superiority test of DOAC will be performed using a one-sided 0.05 significance level and the same two-sided 90% CI for the difference in the event rate of the primary endpoint at 6 months as used for the noninferiority test. When the upper bound of the CI is less than 0, we will conclude that DOAC therapy is superior to LMWH/warfarin in terms of VTE prevention. Because we will perform the superiority test only after the noninferiority of DOAC is demonstrated, the overall type I error rate is maintained at the 0.05 level (one-sided) without splitting alpha.

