### 3.5.2.2. *Planned Interim Analyses*

This study design incorporates several interim analyses and one final analysis for the comparison of the primary endpoint. A 90% two-sided repeated confidence interval (RCI) for the difference in the cumulative incidence rate of VTE at 6 months (DOAC minus Usual Care) between two arms was estimated. We use the critical values based on the Lan-DeMets error spending function corresponding to the truncated version of O'Brien-Fleming boundaries.

Prior to the final analysis, four interim analyses were conducted on September 7, 2018, March 22, 2019, September 9, 2019, and March 25, 2020. Given these interim analyses, the critical value for the final analysis will be 1.710, which corresponds to a one-sided 0.0436 alpha. The confidence coefficient of the 90% two-sided RCI will be 91.28% for the final analysis.

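### The plan gives two critical values for the final primary tests, 1.645 in the decision rules and 1.710 in the interim section, and does not say which one decides

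*Combined protocol and SAP*

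**What the plan says.** **Decision rules (SAP 3.5.2.1; protocol 13.3.1).** The primary analysis estimates the difference in 6-month cumulative incidence with "the corresponding 0.90 confidence interval (CI"). For noninferiority, "we will construct a two-sided 90% confidence interval (CI) for the difference in the cumulative incidence of the primary endpoint at 6 months", and its upper bound must be below 3%. Superiority is tested next, "using a one-sided 0.05 significance level and the same two-sided 90% CI", with the upper bound required to be below 0. Because the tests are ordered, the SAP states that "the overall type I error rate is maintained at the 0.05 level (one-sided) without splitting alpha".

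**General principle (SAP 3.1).** "A 90% two-sided CI corresponds to conducting a statistical test at a one-sided 5% significance level".

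**Interim section (SAP 3.5.2.2; protocol 13.3.2).** The design uses repeated confidence intervals with Lan-DeMets spending of a truncated O'Brien-Fleming type. After four interim analyses, "the critical value for the final analysis will be 1.710, which corresponds to a one-sided 0.0436 alpha". The section adds: "The confidence coefficient of the 90% two-sided RCI will be 91.28% for the final analysis".

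The decision rules do not mention the repeated interval, 1.710, 0.0436 or 91.28%. The interim section does not say that its interval is the one compared with 3% and 0.

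**The concern.** These sections set the threshold for the trial's primary conclusion, and they allow two readings.

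- **Reading (a), literal.** The decision interval is an ordinary 90% CI with critical value 1.645. The one-sided 0.05 stated for superiority and the equivalence in SAP 3.1 support this. The SAP glossary also lists CI separately from the repeated interval, which it enters as "RCT – Repeated Confidence Interval".
- **Reading (b).** The 90% interval in the decision rules is the repeated interval, which the interim section also calls 90% although its coefficient at the final look is 91.28%. The critical value is then 1.710.

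Under (a), the adjustment computed for four looks plays no part in the final decision. The ordering argument in SAP 3.5.2.1 covers two hypotheses tested in sequence. It does not cover five analyses of the same endpoint. Under (b), the overall 0.05 holds. A result whose 90% upper limit lies just below 3%, or just below 0, passes under (a) and fails under (b). If the choice is left open until the data are seen, the primary test is settled after the fact.

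**Working it through.** **1. Reproduce the plan's figures.** From SAP 3.5.2.2, the final critical value is 1.710.
- 1 - Phi(1.710) = 0.04363, which rounds to the stated 0.0436.
- 1 - 2 x 0.0436 = 0.9128, the stated 91.28% (91.27% from unrounded 1.710).

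The interim section is internally consistent. An ordinary two-sided 90% CI has z = 1.645 and one-sided level 0.0500, so the two sections state different nominal levels.

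**2. Distance between the two upper limits.** This is (1.710 - 1.645) x SE = 0.065 x SE. The documents do not give the SE, so it is taken from the 6.1% expected interval length in SAP 2.5, whose confidence level is not stated.

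| Assumption about the 6.1% length | SE (points) | Difference (points) |
|---|---|---|
| used 1.645, n = 668 | 6.1/(2 x 1.645) = 1.854 | 0.121 |
| used 1.710, n = 668 | 6.1/(2 x 1.710) = 1.784 | 0.116 |
| used 1.96, n = 668 | 6.1/(2 x 1.96) = 1.556 | 0.101 |
| used 1.645, modified ITT 10% smaller | 1.854/sqrt(0.9) = 1.955 | 0.127 |
| used 1.645, modified ITT 20% smaller | 1.854/sqrt(0.8) = 2.073 | 0.135 |

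The 10% and 20% reductions are assumptions, because the size of the modified ITT population is not given.

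**3. Cut-offs for the observed difference, with SE = 1.854.**
- Noninferiority: 3 - 1.645 x 1.854 = -0.05 points, against 3 - 1.710 x 1.854 = -0.17 points.
- Superiority: -1.645 x 1.854 = -3.05 points, against -1.710 x 1.854 = -3.17 points.

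An observed difference between the two cut-offs passes one rule and fails the other.

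**4. Overall one-sided error if 1.645 is used at the end.** This applies only if the interim boundaries could have supported a claim. With 1.710 the overall error is 0.05. Moving to 1.645 adds at most the probability that the final statistic falls between the two values:

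0.05 + [Phi(1.710) - Phi(1.645)] = 0.05 + 0.0064 = 0.0564.

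This ceiling needs no information fractions. As an illustration, Lan-DeMets O'Brien-Fleming-type boundaries at one-sided 0.05 were computed by recursive integration for assumed information fractions, with and without an assumed truncation at z = 3:

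| Assumed fractions | Final boundary | Overall error with 1.645 |
|---|---|---|
| 0.20/0.35/0.50/0.70/1 | 1.706-1.709 | 0.0554-0.0556 |
| 0.25/0.40/0.55/0.70/1 | 1.708-1.709 | 0.0555-0.0556 |
| 0.15/0.30/0.50/0.70/1 | 1.706-1.710 | 0.0554-0.0557 |

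These sets are shown because their final boundary is close to the stated 1.710.

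**5. Power at 1.710 with 668 patients, if the table in SAP 2.5 used 1.645.**
- Noninferiority: Phi(1.2816 + 1.645 - 1.710) = 0.888, against the stated 0.900.
- Superiority: Phi(0.6935 + 1.645 - 1.710) = 0.735, against the stated 0.756.

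The table does not reveal which value it used. Scaling its 668-patient powers to 750 gives 0.927 and 0.798 with 1.645, or 0.928 and 0.799 with 1.710. Both pairs are close to the stated 0.927 and 0.797.

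**The case against.** The best reply is that the two sets of figures are the overall and nominal levels of one rule. The interim section directly follows the decision rules and concerns the same endpoint, contrast and final analysis. It calls the interval with a 91.28% coefficient a 90% interval. A final critical value for the primary endpoint has no use other than comparison with 3% and 0, so the literal reading leaves 1.710 without a function. On this view the plan lacks only a cross-reference.

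Much of this is fair. Reading (b) is probably what was meant. The separate glossary entries are weak evidence, since an abbreviation list would normally show both terms. The error inflation is conditional: the documents state no explicit interim efficacy stopping rule, and they attribute the early close of enrollment to the pandemic and an external trial's results, with no mention of a boundary crossing. The fractions in step 4 are assumed, so the 0.0564 ceiling is the firmer figure.

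The text still does not settle the matter. It gives one-sided 0.05 as the level of the superiority test itself, SAP 3.1 equates a 90% CI with a one-sided 5% test, and overall error control is argued from test order alone. A programmer following SAP 3.5.2.1 to the letter would use 1.645.

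**Conclusion.** The concern holds. The primary decision threshold is stated at two levels, and nothing in the protocol or SAP says which governs. It should be fixed, although the numerical effect is small.

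- The upper limits differ by about 0.10 to 0.14 percentage points, given the assumptions about the 6.1% length and the size of the modified ITT population.
- Under reading (b) the overall one-sided error is 0.05. Under reading (a) it is at most 0.0564, and it exceeds 0.05 only if an interim look could have supported a claim.
- Only results whose 90% upper limit falls that close below 3% or 0 would change conclusion.

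The conflict between the sections needs no assumption. Only the sizes do.

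**What to change.** In protocol 13.3.1 and SAP 3.5.2.1, state that the interval compared with 3%, and then with 0, is the final 91.28% repeated confidence interval, with upper limit equal to the estimate plus 1.710 x SE. Replace the final-test level of one-sided 0.05 with one-sided 0.0436, described as giving an overall 0.05 across the interim and final analyses.

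Then make the related text agree:
- Add this exception to SAP 3.1.
- Label any ordinary 90% CI for the primary endpoint as descriptive.
- Correct the glossary abbreviation to RCI.
- State whether the interim boundaries allowed a noninferiority or superiority claim.
- State which critical value the power table used.

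The cost is wording, plus a final interval about 4% wider (1.710/1.645 = 1.04). On a 6.1-point 90% interval this gives 2 x 1.710 x 1.854 = 6.34 points. If the power table used 1.645, the powers to report are 0.888 and 0.735. If it already used 1.710, the stated powers stand.
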